10.1.6. Source Documents

Source documents provide evidence for the existence of the participant and substantiate the integrity of the data collected. Source documents are filed at the investigator's site.

Data reported on the CRF that are transcribed from source documents must be consistent with the source documents or the discrepancies must be explained. The investigator may need to request previous medical records or transfer records, depending on the study. Current medical records must be available.

The definition of what constitutes source data can be found in Section [10.1.5](#).

10.1.7. Study and Site Start and Closure

The study start date is the date on which the clinical study will be open for recruitment of participants.

Site Closure

The sponsor designee reserves the right to close the study site or terminate the study at any time for any reason at the sole discretion of the sponsor. Study sites will be closed upon study completion. A study site is considered closed when all required documents and study supplies have been collected and a study-site closure visit has been performed.

The investigator may initiate study-site closure at any time, provided there is reasonable cause and enough notice is given in advance of the intended termination.

Reasons for the early closure of a study site by the sponsor or investigator may include but are not limited to

- failure of the investigator to comply with the protocol, the requirements of the IRB/IEC or local health authorities, the sponsor's procedures, or GCP guidelines
- inadequate recruitment of participants by the investigator, or
- discontinuation of further study intervention development.

If the study is prematurely terminated or suspended, the sponsor shall promptly inform the investigators, the IECs/IRBs, the regulatory authorities, and any contract research organization(s) used in the study of the reason for termination or suspension, as specified by the applicable regulatory requirements. The investigator shall promptly inform the participants and assure appropriate participant therapy and/or follow-up.

10.1.8. Publication Policy

In accordance with the sponsor's publication policy, the results of this study will be submitted for publication by a peer-reviewed journal if the results are deemed to be of significant medical importance.

10.1.9. Investigator Information

Physicians with a specialty in infectious disease, critical care, or pulmonary disease may participate as investigators.

10.1.10. Long-Term Sample Retention

Sample retention enables use of new technologies, response to regulatory questions, and investigation of variable response that may not be observed until later in the development of the intervention or after the intervention becomes commercially available.

This table describes the retention period for potential sample types.

Sample Type	Custodian	Retention Period After Last Participant Visit
Pharmacogenetics sample	Sponsor or designee	up to 15 years
Exploratory Biomarker Samples	Sponsor or designee	up to 15 years
PK sample	Sponsor or designee	up to 2 years
Immunogenicity (ADA) sample	Sponsor or designee	up to 15 years

10.2. Appendix 2: Clinical Laboratory Tests

- Clinical laboratory tests will be performed according to the SoA. Additional details are provided in the following table for specific laboratory tests.
- Additional tests may be performed at any time during the study as determined necessary by the investigator or required by local regulations.
- Pregnancy testing will be performed according to the SoA.
- The following table describes when the local or central laboratory will be used.
- If the local laboratory results are used to make either a study intervention decision or response evaluation, the results must be recorded in the CRF.
- Laboratory results that could unblind the study will not be reported to study sites or other blinded personnel.
- Protocol-specific requirements for inclusion or exclusion of participants are detailed in Section 5 of the protocol.
- Investigators must document their review of each laboratory safety report.

Clinical Laboratory Tests	Comments
Hematology	Assayed by local laboratory
Hemoglobin	
Hematocrit	
Erythrocyte count (RBCs - red blood cells)	
Mean cell volume	
Mean cell hemoglobin	
Leukocytes (WBCs - white blood cells)	
Differential	
Neutrophils, segmented	
Lymphocytes	
Monocytes	
Eosinophils	
Basophils	
Platelets	
Cell morphology (RBC and WBC)	
Clinical Chemistry	Assayed by local laboratory
Sodium	
Potassium	
Chloride	
Bicarbonate	
Total bilirubin	
Direct bilirubin	Record on Day -1 and repeat if significantly abnormal value
Alkaline phosphatase (ALP)	
Alanine aminotransferase (ALT)	
Aspartate aminotransferase (AST)	
Blood urea nitrogen (BUN)	
Creatinine	

Clinical Laboratory Tests	Comments
Uric acid	Record on Day -1 and repeat if significantly abnormal value
Total protein	
Albumin	
Calcium	
Phosphorus	
Random glucose	
Calculations	Completed locally
Hepatitis B surface antigen	
Hepatitis B surface antibody	
Hepatitis B core antibody (HBcAb)	
Hepatitis C antibody	
HIV	
SARS-CoV-2 viral infection determination	Local laboratory
SARS-CoV-2 point-of-care	
SARS-CoV-2 nasal or nasopharyngeal sample for research purposes	Day 1 sample assayed by Lilly-designated laboratory. Subsequent samples sent to Lilly-designated laboratory for analysis only if the SARS-CoV-2 point-of-care test performed in parallel is positive
SARS-CoV-2 serology	Assayed by Lilly-designated laboratory.
Urinalysis	Assayed by local laboratory
Specific gravity	
pH	
Protein	
Glucose	
Ketones	
Bilirubin	
Urobilinogen	
Blood	
Nitrite	
Microscopy	If dipstick test is abnormal.
Hormones (female)	Assayed by local laboratory.
Serum pregnancy	
Urine pregnancy	
Ethanol/drug screening	Assayed by local laboratory.
Urine or breath ethanol screen	
Urine drug screen	
Pharmacokinetic (PK) Samples	Assayed by Lilly-designated laboratory. Results will not be provided to the study sites.
Pharmacogenetic sample	Assayed by Lilly-designated laboratory. Results will not be provided to the study sites.
Exploratory Biomarker Serum Sample	Assayed by Lilly-designated laboratory. Results will not be provided to the study sites.

Abbreviations: HIV = human immunodeficiency virus; SARS-CoV-2 = severe acute respiratory syndrome coronavirus 2.

10.2.1. Blood Sampling Summary

This table summarizes the approximate number of venipunctures and blood volumes for all blood sampling (screening, safety laboratories, and bioanalytical assays) during the study.

Purpose	Blood Volume per Sample (mL)	Number of Blood Samples	Total Volume (mL)
Screening tests ^a	45	1	45
Clinical laboratory tests ^a	15	7	105
SARS-CoV-2 serology	10	5	50
Pharmacokinetics	4	11	44
Immunogenicity	10	4	40
Blood discard for cannula patency	1	5	5
Pharmacogenetics	10	1	10
Serum for exploratory biomarkers	10	5	50
Total			349
Total for clinical purposes (rounded up to nearest 10 mL)			350

^a Additional samples may be drawn if needed for safety purposes.

10.3. Appendix 3: Adverse Events: Definitions and Procedures for Recording, Evaluating, Follow-up, and Reporting

10.3.1. Definition of AE

AE Definition

An AE is any untoward medical occurrence in a clinical study participant temporally associated with the use of study intervention, whether or not considered related to the study intervention.

NOTE: An AE can therefore be any unfavorable and unintended sign (including an abnormal laboratory finding), symptom, or disease (new or exacerbated) temporally associated with the use of study intervention.

Events Meeting the AE Definition

- Any abnormal laboratory test results (hematology, clinical chemistry, or urinalysis) or other safety assessments (for example, ECG, radiological scans, vital signs measurements), including those that worsen from baseline, considered clinically significant in the medical and scientific judgment of the investigator (i.e., not related to progression of underlying disease).
- Exacerbation of a chronic or intermittent pre-existing condition including either an increase in frequency and/or intensity of the condition.
- New conditions detected or diagnosed after study intervention administration even though it may have been present before the start of the study.
- Signs, symptoms, or the clinical sequelae of a suspected drug-drug interaction.
- Signs, symptoms, or the clinical sequelae of a suspected overdose of either study intervention or a concomitant medication. Overdose per se will not be reported as an AE/SAE unless it is an intentional overdose taken with possible suicidal/self-harming intent. Such overdose should be reported regardless of sequelae.

Events NOT Meeting the AE Definition

- Lack of drug effect is not an AE in clinical studies, because the purpose of the clinical study is to establish treatment effect.
- The following study-specific clinical events related to COVID-19 are exempt from AE reporting unless the investigator deems the event to be related to the administration of intervention:
 - Hypoxemia due to COVID-19 requiring supplemental oxygen;
 - Hypoxemia due to COVID-19 requiring non-invasive ventilation or high flow oxygen devices;

- Respiratory failure due to COVID-19 requiring invasive mechanical ventilation or ECMO
- Any clinically significant abnormal laboratory findings or other abnormal safety assessments which are associated with the underlying disease under study, unless judged by the investigator to be more severe than expected for the participant's condition.
- The disease/disorder being studied or expected progression, signs, or symptoms of the disease/disorder being studied, unless more severe than expected for the participant's condition.
- Medical or surgical procedure, such as endoscopy or appendectomy. The condition that leads to the procedure is the AE.
- Situations in which an untoward medical occurrence did not occur (social and/or convenience admission to a hospital).
- Anticipated day-to-day fluctuations of pre-existing disease(s) or condition(s) present or detected at the start of the study that do not worsen.

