2.3. Benefit/Risk Assessment

There is no anticipated therapeutic benefit for the participants.

The maximum planned dose of LY3832479 in this study is 1000 mg SC. This is lower than the maximum dose delivered IV in previous studies.

Potential risks related to SC injections of LY3832479 are as follows:

- Hypersensitivity reactions and ISRs: Study participants will be in-house for the first 7 days after dosing, which will enable close monitoring for hypersensitivity reactions and ISRs post-injection.
- Antibody-dependent enhancement of viral replication in case any of these healthy volunteers contract a SARS-CoV-2 infection while they still have significant LY3832479 exposure after dosing: This phenomenon has been observed with some other viruses including the dengue virus, but is only a theoretical risk without clinical evidence in the case of respiratory coronaviruses (Graham 2020). In addition, LY3832479 was specifically engineered to avoid this risk as explained in Section 2.2.

- Unknown risks related to on-target and off-target toxicity. These risks are low due to the
 - fact that LY3832479 targets a foreign protein
 - human origin of LY3832479 (the LALA mutations do not involve the RBD of LY3832479), and
 - absence of binding in the TCR studies performed in humans and monkeys.

Given the totality of data on LY3832479, the overall benefit/risk assessment of this study is considered favorable.

More detailed information about the known and expected benefits and risks and reasonably expected AEs of LY3832479 may be found in the IB.

3. Objectives and Endpoints

Objectives	Endpoints
Primary	
To determine the PK of single SC doses of LY3832479 in healthy participants	AUC(0-∞) and C _{max}
Secondary	
To describe safety and tolerability following single SC doses of LY3832479 in healthy participants	Incidence of spontaneously reported AEs, TEAEs, and SAEs; vital signs; clinical laboratory results
Exploratory	
To assess ISRs following single SC doses of LY3832479 in healthy participants	Characterization and measurement of incidence and severity of ISRs (including injection site pain) using data collected from the ISR assessment, as well as the exploratory tool (Scarletred)
To determine the immunogenicity of LY3832479 following single SC doses in healthy participants	Incidence of TEADA

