10.3.2. Definition of SAE

Please note: If an event is not an AE per definition above, then it cannot be an SAE.

An SAE is defined as any AE that:

a. Results in death

b. Is immediately life-threatening

The term 'life-threatening' in the definition of 'serious' refers to an event in which the participant was at risk of death at the time of the event. It does not refer to an event, which hypothetically might have caused death, if it were more severe.

c. Requires inpatient hospitalization or prolongation of existing hospitalization

- In general, hospitalization signifies that the participant has been admitted to hospital for > "23 hour observation" and/or treatment that would not have been appropriate in the physician's office or outpatient setting. Complications that occur during hospitalization are AEs. If a complication prolongs hospitalization or fulfills any other serious criteria, the event is serious. When in doubt as to whether "hospitalization" occurred or was necessary, the AE should be considered serious.
- Hospitalization for elective treatment of a pre-existing condition that did not worsen from baseline is not considered an AE.

d. Results in persistent disability/incapacity

- The term disability means a substantial disruption of a person's ability to conduct normal life functions.
- This definition is not intended to include experiences of relatively minor medical significance such as uncomplicated headache, nausea, vomiting, diarrhea, influenza,

and accidental trauma (for example, sprained ankle) which may interfere with or prevent everyday life functions but do not constitute a substantial disruption.
e. Is a congenital anomaly/birth defect
f. Other situations: 
• Medical or scientific judgment should be exercised in deciding whether SAE reporting is appropriate in other situations such as important medical events that may not be immediately life-threatening or result in death or hospitalization but may jeopardize the participant or may require medical or surgical intervention to prevent one of the other outcomes listed in the above definition. These events should usually be considered serious.
○ Examples of such events include intensive treatment in an emergency room or at home for allergic bronchospasm, blood dyscrasias or convulsions that do not result in hospitalization, or development of drug dependency or drug abuse.

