10.3.3. Recording and Follow-Up of AE and/or SAE

AE and SAE Recording

When an AE/SAE occurs, it is the responsibility of the investigator to review all documentation (for example, hospital progress notes, laboratory reports, and diagnostics reports) related to the event.

The investigator will then record all relevant AE/SAE information in the CRF.

It is not acceptable for the investigator to send photocopies of the participant's medical records to Sponsor or designee in lieu of completion of the AE/SAE CRF page.

There may be instances when copies of medical records for certain cases are requested by Sponsor or designee. In this case, all participant identifiers, except the participant number, will be redacted on the copies of the medical records before submission to Sponsor or designee.

The investigator will attempt to establish a diagnosis of the event based on signs, symptoms, and/or other clinical information. Whenever possible, the diagnosis (not the individual signs/symptoms) will be documented as the AE/SAE.

Assessment of Intensity/Severity

The investigator will make an assessment of intensity for each AE and SAE reported during the study and assign it to one of the following categories, which together with serious criteria on the AE CRF ("results in death" and "life-threatening"), are aligned with the Division of AIDS Table for Grading the Severity of Adult and Pediatric Adverse Events, version 2.1 (DAIDS 2017).

Mild: Mild symptoms causing no or minimal interference with usual social and functional activities, with intervention not indicated.

Moderate: Moderate symptoms causing greater than minimal interference with usual social and functional activities, with intervention indicated.

Severe: Severe symptoms causing inability to perform usual social and functional activities, with intervention or hospitalization indicated.

An event is defined as 'serious' when it meets at least 1 of the predefined outcomes as described in the definition of an SAE, NOT when it is rated as severe.

Assessment of Causality

The investigator is obligated to assess the relationship between study intervention and each occurrence of each AE/SAE.

A "reasonable possibility" of a relationship conveys that there are facts, evidence, and/or arguments to suggest a causal relationship, rather than a relationship cannot be ruled out.

The investigator will use clinical judgment to determine the relationship.

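### Protocol 10.3.1 keeps three COVID-19 respiratory complications out of AE and SAE status when judged unrelated, a rule ill suited to healthy volunteers that may leave a case out of the AE/SAE incidence

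*Protocol*

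**What the plan says.** Protocol 10.3.1 first gives a causality-neutral definition: an AE is any untoward occurrence temporally associated with the intervention, "whether or not considered related to the study intervention". Among the events that qualify it lists "New conditions detected or diagnosed after study intervention administration".

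Under its heading for events that do not meet the definition, it then says that certain "study-specific clinical events related to COVID-19 are exempt from AE reporting unless the investigator deems the event to be related" to the administration of the intervention. Three events follow:

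- hypoxemia due to COVID-19 needing supplemental oxygen;
- hypoxemia due to COVID-19 needing non-invasive ventilation or high-flow oxygen;
- respiratory failure due to COVID-19 needing invasive ventilation or ECMO.

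The same list also excludes "The disease/disorder being studied or expected progression, signs, or symptoms of the disease/disorder being studied", unless more severe than expected for the participant's condition.

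Protocol 10.3.2 carries the exemption through to seriousness: "If an event is not an AE per definition above, then it cannot be an SAE". That section also states, under hospitalization, "Complications that occur during hospitalization are AEs". Protocol 10.3.3 says that, whenever possible, "the diagnosis (not the individual signs/symptoms) will be documented as the AE/SAE".

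The incidence of AEs, TEAEs and SAEs is part of the secondary endpoint (Protocol 3; SAP 4.2). SAP 9.4.1 tabulates TEAEs by treatment and severity, for all causalities and for related events, and lists SAEs.

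**The concern.** In a trial of COVID-19 patients, an exemption of this kind keeps progression of the disease under treatment out of the AE tables. This trial has no such disease. Protocol 4.2 explains that healthy participants are studied instead of patients, Protocol 5.2 excludes current SARS-CoV-2 infection, and Protocol 8.1 has no efficacy assessments. COVID-19 after dosing would be a new event. The protocol foresees it: Section 4.1.3 allows home visits for participants with suspected or confirmed infection.

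The exemption also touches a named risk. Section 2.3 lists "Antibody-dependent enhancement of viral replication in case any of these healthy volunteers contract a SARS-CoV-2 infection" while still exposed to the antibody. The protocol calls this theoretical, but enhancement would be expected to appear as worse COVID-19, and worse COVID-19 is what is exempted.

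The relatedness exception is a thin safeguard. The investigator is blinded (Section 6.3). Section 10.3.3 requires facts, evidence or arguments that suggest a causal relationship, and it is not enough that one cannot be ruled out. A single case could well be judged unrelated. It could then be missing from the all-causality incidence, and the 24-hour SAE reporting in Section 8.3.1 might not be triggered.

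**Working it through.** The documents state no figure that depends on this rule, so there is none to reproduce. The check follows one case through the text and then gives its weight in the tables.

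**Following one case.** Take a participant with post-dose respiratory failure due to COVID-19 that needs invasive ventilation, judged unrelated.

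1. *The complication.* The general definition in 10.3.1 makes it an AE whatever its cause. The exemption in 10.3.1 removes it, and 10.3.2 then bars SAE status. The hospitalization text in 10.3.2 points the other way. Because the exemption is an explicit carve-out under its own heading, it is best read as a deliberate choice that fits poorly, not as a plain contradiction.
2. *The diagnosis.* The exemption does not name COVID-19 itself. As a newly diagnosed condition it is probably an AE (10.3.1, 10.3.3), and an SAE if it leads to hospitalization or is life-threatening (10.3.2).
3. *The second exclusion.* The bullet on the disease being studied could remove the diagnosis too, unless it is more severe than expected. In a healthy-volunteer study neither the disease being studied nor the expected severity has a clear meaning.
4. *The tables.* If the diagnosis is recorded, the participant is counted in the SAP 9.4.1 tables. If it is not, the participant is absent from them.
5. *Other outputs.* SAP 9.1 lists all databased data, and SAP 9.4.10 lists SARS-CoV-2 screening, serology and point-of-care results. Neither listing feeds the AE or SAE counts.

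**Weight of one omitted case.** Inputs are at least 9 per cohort, split 7 active to 2 placebo (Protocol 4.1.1), two cohorts, and a maximum of 22 (Protocol 1.1). The minimum total is 2 × 9 = 18, so up to 22 − 18 = 4 participants are unallocated.

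| Group | Share of one case |
|---|---|
| Active dose group, minimum size | 1/7 = 14.3% |
| Active dose group, if all 4 extra are active in that group (assumption) | 1/(7 + 4) = 1/11 = 9.1% |
| Both active groups, minimum size | 1/14 = 7.1% |
| Pooled placebo, minimum size | 1/4 = 25% |
| All participants, minimum | 1/18 = 5.6% |
| All participants, maximum | 1/22 = 4.5% |

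In a 7-person dose group, counting the case moves the observed incidence from 0/7 (exact Clopper-Pearson 90% interval 0% to 34.8%) to 1/7 (0.7% to 52.1%).

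**Chance that a case arises.** The documents give no rate. With an assumed per-participant risk p over follow-up, P(at least one case) = 1 − (1 − p)^n:

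| Assumed p | n = 18 | n = 22 |
|---|---|---|
| 0.1% | 1.8% | 2.2% |
| 0.5% | 8.6% | 10.4% |
| 1% | 16.5% | 19.8% |
| 2% | 30.5% | 35.9% |

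These are chances of a case, not of an omission. An omission also needs an unrelated judgment and an unrecorded diagnosis, so for any given p they are upper limits.

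**Time at risk outside the unit.** Discharge is on Day 7 and follow-up ends on Day 85 (Protocol 4.1.2, 4.1.3): 85 − 7 = 78 days, and 78/85 = 91.8%. This describes the opportunity for infection in the community and says nothing about recording.

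**The case against.** The strongest reply is that the case would be counted anyway. The exemption covers only hypoxemia and respiratory failure. It does not name infection, hospitalization or death. Sites are told to record the diagnosis, so a hospitalized participant would ordinarily appear as a serious COVID-19 AE. The exclusion for the disease being studied arguably has nothing to act on here, and respiratory failure in someone who entered healthy readily counts as more severe than expected. Suspected enhancement can be reported as related, and the investigator must consult the Investigator's Brochure on causality. AE review and COVID-19 screening take place at every follow-up visit, so a case is unlikely to go unseen.

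Much of this stands, and it is why the conclusion is that a case may be left out, not that it will be. It also stands that the shares above are the weight of any one missing participant, and that the protocol does not grade the three events.

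It does not remove the rule. The text still tells sites that these complications are not AEs, and the sentence on complications during hospitalization tells them the opposite. Even with the diagnosis recorded, the events that would make it serious are the exempted ones, so a site could record it as non-serious. Capture then rests on a blinded causality judgment and on a bullet with no clear meaning in this population.

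**Conclusion.** The concern holds and should be fixed. The exemption is a stated design choice that does not suit healthy volunteers, and it sits poorly with the protocol's own causality-neutral definition. Its reach is narrow: three event types, only when judged unrelated, with a participant lost from the incidence only if the COVID-19 diagnosis is not itself recorded as an AE. The probability of that cannot be derived from the documents and is likely small. If it happened, one case would be 9% to 14% of an active dose group, the lower figure resting on the allocation assumption above. The primary PK endpoints, events judged related and the temporary stopping criteria in Protocol 6.6.3, which count only related AEs, are unaffected. Confidence is medium, because the outcome depends on how a site reads the exclusion for the disease being studied.

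**What to change.** Delete the three-event COVID-19 exemption from Protocol 10.3.1. State there that COVID-19 arising after dosing, and its complications, are recorded as AEs, and as SAEs when the criteria in 10.3.2 are met, regardless of causality and notwithstanding the bullets on the disease under study. This also removes the tension with the hospitalization text in 10.3.2.

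The events then enter the existing SAP 9.4.1 tables and SAE listing with no new analysis. A listing of COVID-19 severity in SAP 9.4.10 would be useful but is optional.

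The cost is a wording amendment to one protocol section and at most a few additional AE or SAE records. The change concerns reporting only and does not alter clinical management.
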